5.9.4 Return or Destruction of Study Drug

All study drug/placebo left over will be returned to Gillette Pharmacy for final reconciliation and destruction.

6.0 Study Procedures

Outline of procedure plan

1. Recruitment from clinics including: chronic care, neurology, gastroenterology, and pain
2. History and physical examination completed as part of routine assessment and management for chronic irritability
3. Determine if evaluation for potentially treatable causes of chronic irritability has been completed.
4. Parental consent
5. Parental questionnaire #1 and NCCPC-R rating 3 typical irritable events
6. Randomization: gabapentin or placebo
7. Titration schedule
8. Day 6 — phone call by study staff (or closest week day)
9. Day 13 — NCCPC-R, questionnaire #2, and phone call follow-up (or closest week day)
10. Day 24 — NCCPC-R, questionnaire #2, and phone call follow-up (or closest week day)
If no improvement (dose 40 mg/kg/day) begin taper early(step #11) and set up visit with Research Coordinator (Step #12)
11. Day 29 — Begin medication taper
12. Day 34 to 38 — Family comes in to meet with the Research Coordinator. Subject is weighed. Perceived benefits and side effects of the drug are discussed. Report any concerns to the PI, if any. Subject is provided new drug at this visit. The old bottle will be taken back, along with the dosing chart. Remaining drug will be measured.
13. Day 38 — Crossover
14. Repeat steps 7 —11
15. At completion Research Coordinator contacts family by telephone to discuss perceived benefits/side effects of round 2 drug. Reports concerns to PI, if any

Parents complete one questionnaire #1, four questionnaires #2, and six NCCPC-R

Questionnaire # 1: includes 60 questions that require identifying the appropriate response from the items listed and 5 questions that require a written response.

Information obtained includes: frequency and duration of pain episodes along with associated gastrointestinal symptoms and sleep disturbance. The questionnaire takes approximately 15 minutes to complete.

Questionnaire #2: includes 24 questions that require identifying the appropriate response from the items listed and 2 questions that require a written response. Information obtained includes: frequency and duration of pain episodes along with associated gastrointestinal symptoms and sleep disturbance. The questionnaire takes approximately 5 minutes to complete.

NCCPC-R: Pain behavior in nonverbal neurologically impaired children can be measured using the Non-Communicating Children's Pain Checklist-Revised (NCCPC-R).^{10, 11} The scale consists of seven domains including Vocal, Eating/Sleeping, Social/Personality, Facial Expression, Activity, Body/Limbs, and Physiological. The NCCPC-R has shown validity and reliability for everyday pain among children with developmental disabilities and was applied to study the incidence of pain in children with severe neurological impairments. Cut-off scores based on receiver operating characteristics suggest a score of 7 or greater on the NCCPC-R as indicative of pain in such children. The NCCPC-R takes approximately 5 minutes to complete.

Schedule of Events

Day	Pre-screen	Informed Consent	Medical History	Physical Exam	Phone Check	NCCPC-R	Q1	Q2
0	X	X	X	X		X	X	
6					X			
13					X	X		X
24					X	X		X
28					X			
34-37			X			X		X
38					X			
44					X			
51					X	X		X
62					X	X		X
76					X			

The Day 0 visit occurs as an office visit at the Gillette Children's Specialty Healthcare facility. A medical history and physical examination will be completed as part of routine assessment and management for chronic irritability. Determine if evaluation for potentially treatable causes of chronic irritability has been completed. The first round of drug will be dispensed. Families will be asked to mark off each dose they take out of the bottle with an X on the dosing sheet. Another visit with the research coordinator will occur once the drug has been tapered, during the washout period. During that visit, the subject will be re-weighed, the old drug bottle will be taken and the remaining drug measured, and

the old dosing sheet will be taken. Any benefits or side effects will be discussed at this visit, and the new drug bottle will be dispensed. Once drug has been tapered the second time, patients will be instructed to return the bottle when they return for their next standard of care appointment at Gillette Children's Specialty Healthcare.

Unscheduled visits

If any unscheduled visits occur due to side effects, another physical exam will be done and side effects will be recorded. Standard of care treatment will be administered for side effects. The NCCPR-C and Questionnaire #2 will be done as well.

7.0 Statistical Plan

7.1 Sample Size Determination

Power Calculations: A minimum sample size of 40 patients was determined by estimating a 15 point difference using the NCCPR-R pain assessment tool (90 points total) pre and post gabapentin, with a SD of 25 and within-person correlation of 0.6, accounting for recruitment and retention.

7.2 Statistical Methods

Simple descriptive statistics will be utilized to compare differences between the treatment and placebo groups with respect to frequency and duration of pain episodes, and frequency of gastrointestinal and sleep problems. Parent/caregiver reported questionnaires will be compared between groups. The NCCPR-R assessments will be scored and compared between groups, with a 15 point difference considered a significant difference.

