Reference therapy	Reference therapy for this study is the placebo as there is no standard of care.
Statistical Methodology	The study will utilize non-parametric descriptive statistics to compare subject questionnaire responses after drug and placebo exposures.

Formatted: Highlight

Formatted: Highlight

Formatted: Highlight

Formatted: Highlight

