3.0 Study Design

3.1 General Study Design

The design of this study is a prospective, randomized, double blind, placebo-controlled, crossover clinical trial. The study will involve a 22-day medication/placebo titration period, 7-day stable dosing, 9-day taper and washout, followed by crossover. The length of the study is 12 months.

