4.0 Subject Selection and Withdrawal

4.1 Inclusion Criteria

Subjects are eligible to participate in the study if all of the following conditions exist:

1. Male or female, age 1 month to 16 years at enrollment
2. Neurological impairment defined as subnormal (-2 S.D.) motor and/or cognitive ability from a variety of etiologies
3. Chronic irritability defined as symptoms suggesting pain to the child's caregiver occurring recurrently over a 4-week or greater time period
4. Subject must have an acceptable surrogate capable of giving consent on the subject's behalf

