5.3 Method for Assigning Subjects to Treatment Groups

A randomization table will be made before the study begins. Each patient added will be entered into their group as the randomization table dictates. This table will be kept in the pharmacy, and a copy will be maintained by the research coordinator to keep track of which group each subsequent subject will be assigned. Access to the table with patient names and doses of drug or placebo will be available in the pharmacy 24 hours x 7 days per week for safety precautions and unblinding.

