7.3 Subject Population(s) for Analysis

The subject population to be analyzed includes all protocol compliant subjects. Subjects who are not compliant with the protocol will be withdrawn as described in Section 5.5

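### Section 7.2 compares gabapentin with placebo between groups in a two-period crossover and ignores period and sequence, so the difference judged against 15 points moves with any imbalance in the analysed sequences

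*SAP*

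**What the plan says.** SAP section 3.1 fixes the design: "The design of this study is a prospective, randomized, double blind, placebo-controlled, crossover clinical trial". Section 7.1 plans 40 patients from a 15-point NCCPC-R difference, an SD of 25 and a within-person correlation of 0.6, so the sizing takes each child as his or her own control.

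Section 7.2 is worded differently. For pain episodes and for gastrointestinal and sleep problems: "Simple descriptive statistics will be utilized to compare differences between the treatment and placebo groups". For the pain scale: "The NCCPR-R assessments will be scored and compared between groups, with a 15 point difference considered a significant difference". The Study Summary adds: "The study will utilize non-parametric descriptive statistics to compare subject questionnaire responses after drug and placebo exposures". None of these sentences mentions period, sequence or a within-child estimate, and no other part of the document does.

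On allocation, section 5.3 says "A randomization table will be made before the study begins" and "Each patient added will be entered into their group as the randomization table dictates". It gives no ratio, block or number per sequence, and sections 5.4 and 5.8 add none. On the analysis set, section 7.3 says "The subject population to be analyzed includes all protocol compliant subjects". Under section 5.5 a child who misses more than three days of doses is non-compliant and is withdrawn.

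**The concern.** In a two-period crossover every child contributes one gabapentin and one placebo period, and the order is what is randomized. Anything that changes scores between the two periods for all children enters each child's gabapentin − placebo difference. Its sign depends on the order. It cancels from the pooled mean only if the two sequences are of equal size among the children analysed. Section 7.2 treats the data as two parallel arms, so nothing removes the shift when the sizes differ.

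This matters more than usual here because 7.2 plans no test and no interval. The observed difference is set directly against 15 points, so an error in the point estimate passes straight into the conclusion.

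**Working it through.** **Inputs.** From 7.1: SD 25, within-person correlation 0.6, difference 15, N = 40. From the Study Summary: 40 evaluable. Not in the documents: the period shift P (assumed 5, 10 or 15 points) and the sequence sizes (several splits shown).

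**The plan's own figure.** SD of a within-child difference = 25 × √(2 × (1 − 0.6)) = √500 = 22.36. A paired comparison of 15 points at two-sided 5% needs ((1.96 + 0.8416) × 22.36/15)² = 17.4, so 18 children for 80% power; the same formula gives 24 for 90%. With the t distribution the numbers are 20 and 26. Alpha, power and the dropout allowance are not stated, so 40 can be neither reproduced uniquely nor refuted. It would fit, for example, 26/(1 − 0.35) = 40. The point below does not depend on this.

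**Bias.** Let P be period 2 minus period 1, the same for all children, with no carryover, and let the true gabapentin − placebo difference be τ.

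- Placebo-first children have gabapentin in period 2, so their mean difference is τ + P.
- Gabapentin-first children have it in period 1, so their mean difference is τ − P.
- Pooled over children with both periods: τ + P × (n placebo-first − n gabapentin-first)/N.

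Absolute bias in points for N = 40:

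| Split | P = 5 | P = 10 | P = 15 |
|---|---|---|---|
| 20:20 | 0 | 0 | 0 |
| 22:18 | 0.5 | 1.0 | 1.5 |
| 24:16 | 1.0 | 2.0 | 3.0 |
| 26:14 | 1.5 | 3.0 | 4.5 |
| 28:12 | 2.0 | 4.0 | 6.0 |

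At 24:16 this is 7%, 13% and 20% of the 15 points. With P = 10, a true difference of 13 would be expected to read as 15 or 11, depending on which sequence is larger.

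**How likely is such a split?** If the table is simple 1:1 randomization (an assumption), Binomial(40, 0.5) gives 12.5% for exactly 20:20, 26.8% for 24:16 or worse and 8.1% for 26:14 or worse. The mean absolute imbalance is 12.5% of N, so a 10-point shift gives 1.25 points of bias on average, in absolute size.

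**Equal sequences.** At 20:20 the shift cancels, and the true standard error stays at 22.36/√40 = 3.54. The SD computed from unadjusted differences becomes √(500 + P² × 40/39), which is 22.9, 24.5 and 27.0 for P = 5, 10 and 15. The computed standard errors are 3.63, 3.88 and 4.27.

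**Simulation check.** 100,000 trials, no drug effect, P = 10. The mean absolute bias was 2.0 at 24:16 and 4.0 at 28:12. At 20:20 the estimate was unbiased with a true SD of 3.53, against a mean computed standard error of 3.86. An unadjusted paired t-test, which 7.2 does not plan, would reject in 3.2% of trials at 20:20, 6.1% at 24:16 and 15.7% at 28:12.

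**With adjustment for period.** Half the difference between sequences in mean (period 1 − period 2) score has no period bias at any split. Its standard error at 20:20 is 3.54. At 24:16 it is ½ × √(500 × (1/24 + 1/16)) = 3.61.

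**The case against.** The strongest reply is that randomizing the order is itself how a crossover handles period. Over repeated 1:1 randomizations the period effect averages to zero, so the planned comparison is not systematically biased. That is correct. What remains is conditional: this trial is run once, and its split may be unequal.

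Five stronger readings are tempting, and the document does not support them.

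- **The allocation is unblocked.** Section 5.3 is silent; the pharmacy's table may well be blocked. The 27% holds only if it is not.
- **Compliance exclusions must destroy balance.** They do so only if losses differ between sequences. Section 7.3 permits this but does not make it certain.
- **The document itself predicts a period shift.** Section 3.3 hypothesises that escalation of symptoms is related in time to surgery; it says nothing of recovery. Section 4.1 requires symptoms "occurring recurrently over a 4-week or greater time period" and sets no minimum NCCPC-R score. Regression to the mean would also fall mainly between Day 0 and period 1, not between the two periods. A shift is possible, but its size is not documented.
- **A period effect adds noise even with equal sequences.** It does not change the true variance of the estimate. Only a standard error computed from unadjusted differences is inflated, which is conservative, and 7.2 plans neither an interval nor a test.
- **The Study Summary implies a paired comparison.** Comparing responses after each exposure could be read as within-child. Even so, period is still left out.

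It is also fair to say that the bias is small against 15 points at mild imbalance.

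**Conclusion.** The point holds in a limited form. Section 7.2 describes a parallel-group comparison for a crossover that 7.1 sized on within-person correlation, and it makes no allowance for period or sequence. The pooled difference then carries a bias of P × (n placebo-first − n gabapentin-first)/N in the split analysed, and that difference is what 7.2 sets against 15 points. For assumed shifts of 5 to 15 points the bias at 24:16 is 1.0 to 3.0 points; it is zero at 20:20. These figures assume an additive shift common to all children, no carryover and 40 children with both periods. The missing period term in 7.2 is the firm part. The lack of a stated sequence balance in 5.3 is secondary, because it is only silence. The expected effect is modest, but removing it costs almost nothing.

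**What to change.** **Section 7.2, NCCPC-R.** Estimate the treatment effect within child with adjustment for period: half the difference between the two sequences in mean (period 1 − period 2) score, signed as gabapentin − placebo. A linear model with child, period and treatment is equivalent. Compare this estimate with the 15 points. Build each child's period score from assessments made in both periods: the Schedule of Events has Days 13 and 24 against Days 51 and 62, while Days 34-37 have no counterpart in period 2.

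**Section 7.2, questionnaires.** Many items are answered by choosing a listed response, so a linear model does not suit them. Use a period-adjusted rank comparison for ordinal items and a categorical analogue for the rest, in line with the non-parametric approach in the Study Summary.

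**Reporting.** Show NCCPC-R and questionnaire results by sequence and period, with the number of children analysed in each sequence.

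**Section 5.3, minor.** State that the table is blocked by sequence, if it is not already. Blocking alone is not enough, because the compliant-only set can still be unbalanced.

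**Cost.** Wording and one degree of freedom. At 24:16 the standard error rises from 3.54 to 3.61. No extra children or visits are needed.

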7.3 Subject Population(s) for Analysis

The subject population to be analyzed includes all protocol compliant subjects. Subjects who are not compliant with the protocol will be withdrawn as described in Section 5.5

8.0 Safety and Adverse Events

8.1 Definitions

Adverse Event

An *adverse event* (AE) is any symptom, sign, illness or experience that develops or worsens in severity during the course of the study. Intercurrent illnesses or injuries should be regarded as adverse events. Abnormal results of diagnostic procedures are considered to be adverse events if the abnormality:

- results in study withdrawal.
- is associated with a serious adverse event.
- is associated with clinical signs or symptoms.
- leads to additional treatment or to further diagnostic tests.
- is considered by the investigator to be of clinical significance.

Serious Adverse Event

A ***serious adverse event (SAE)*** is any AE that is:

- fatal.
- life-threatening.
- requires or prolongs hospital stay.
- results in persistent or significant disability or incapacity.
- a congenital anomaly or birth defect.

Important medical events may be considered SAEs. Important medical events are those that may not be immediately life threatening, but are clearly of major clinical significance. They may jeopardize the subject, and may require intervention to prevent one of the other serious outcomes noted above. For example, drug overdose or abuse, a seizure that did not result in in-patient hospitalization, or intensive treatment of bronchospasm in an emergency department would typically be considered serious.

Adverse Event Reporting Period

The study period during which adverse events must be reported is normally defined as the period from the initiation of any study procedures to the end of the study treatment follow-up. For this study, the study treatment follow-up is defined as 30 days following the last administration of study treatment.

Preexisting Condition

A preexisting condition is one that is present at the start of the study. A preexisting condition should be recorded as an adverse event if the frequency, intensity, or the character of the condition worsens during the study period.

General Physical Examination Findings

At screening, any clinically significant abnormality should be recorded as a preexisting condition. At the end of the study, any new clinically significant findings/abnormalities that meet the definition of an adverse event must also be recorded and documented as an adverse event.

Post-study Adverse Event

All unresolved adverse events should be followed by the investigator until the events are resolved, the subject is lost to follow-up, or the adverse event is otherwise explained. At the last scheduled visit, the investigator should instruct each subject to report any subsequent event(s) that the subject, or the subject's personal physician, believes might reasonably be related to participation in this study.

Abnormal Laboratory Values

A clinical laboratory abnormality should be documented as an adverse event if any one of the following conditions is met:

- The laboratory abnormality is not otherwise refuted by a repeat test to confirm the abnormality
- The abnormality suggests a disease and/or organ toxicity
- The abnormality is of a degree that requires active management; e.g. change of dose, discontinuation of the drug; more frequent follow-up assessments, further diagnostic investigation, etc.

Hospitalization, Prolonged Hospitalization or Surgery

Any adverse event that results in hospitalization or prolonged hospitalization should be documented and reported as a serious adverse event unless specifically instructed otherwise in this protocol. Any condition responsible for surgery should be documented as an adverse event if the condition meets the criteria for an adverse event.

Neither the condition, hospitalization, prolonged hospitalization, nor surgery are reported as an adverse event in the following circumstances:

- Hospitalization or prolonged hospitalization for diagnostic or elective surgical procedures for a preexisting condition. Surgery should not be reported as an outcome of an adverse event if the purpose of the surgery was elective or diagnostic and the outcome was uneventful.
- Hospitalization or prolonged hospitalization required to allow efficacy measurement for the study.
- Hospitalization or prolonged hospitalization for therapy of the target disease of the study, unless it is a worsening or increase in frequency of hospital admissions as judged by the clinical investigator.

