8.5 Stopping Rules.....	36
8.6 Medical Monitoring	36
9.0 Data Handling and Record Keeping	36
9.1 Confidentiality	36
9.2 Source Documents	37
9.3 Case Report Forms.....	37
9.4 Records Retention.....	37
10.0 Study Monitoring, Auditing, and Inspecting	37
10.1 Study Monitoring Plan.....	37
10.2 Auditing and Inspecting.....	38
11.0 Ethical Considerations	38
12 Study Finances	39
12.1 Funding Source	39
12.2 Conflict of Interest	39
12.3 Subject Stipends or Payments	39
13 Publication Plan	39
14 References.....	39
15 Attachments	40

List of Abbreviations

AE	Adverse Event
CFR	Code of Federal Regulations
CRF	Case Report Form
FDA	Food and Drug Administration
GCP	Good Clinical Practice
HIPAA	Health Insurance Portability and Accountability Act of 1996
ICH	International Conference on Harmonization
IDS	Investigational Drug Service
IRB	Institutional Review Board
ITT	Intent to Treat
NCCPC-R	Non-Communicating Children's Pain Checklist-Revised
PHI	Protected Health Information
REPA	Report of External Professional Activities
SAE	Serious Adverse Event
UPIRTSO	Unanticipated Problems Involving Risk to Subjects or Others

Study Summary

Title	A phase II, randomized, placebo-controlled, double blind, cross-over, study of the effects of Gabapentin on chronic irritability in neurologically impaired children
Short Title	Effects of Gabapentin on chronic irritability in neurologically impaired children.
Phase	Phase II
Methodology	The study is a randomized, placebo-controlled cross-over.
Study Duration	The estimated duration of the study is 12 months
Study Center(s)	This is a single center study to be conducted at Gillette Children's Specialty Hospital, [name].
Objectives	To determine if gabapentin provides symptom relief for chronic irritability in neurologically impaired children despite medical management for identified sources of symptoms or if no etiology is identified.
Number of Subjects	40 evaluable subjects
Diagnosis and Main Inclusion Criteria	Neurological impairment and chronic irritability suggesting pain.
Study Product, Dose, Route, Regimen	Gabapentin (Neurontin®), to be administered as an oral solution titrated over a 22 day period, followed by a 7 day stable dose period (40 mg/kg/day over 3 dosages), followed by a 9 day taper and washout period
Duration of administration	Subjects will receive drug for 34 days, and placebo for 34 days, with a 3 day washout period in between.

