5.2 Treatment Regimen

Doses will be given in liquid form through gastrointestinal tubes (if the child already has one) or orally. Children will be put on the following dosage regimen:

Day	Morning	Afternoon	Evening
1 - 3			5 mg/kg
4 - 6	2.5 mg/kg	2.5 mg/kg	5 mg/kg
7 - 9	2.5 mg/kg	2.5 mg/kg	10 mg/kg
10 - 12	5 mg/kg	5 mg/kg	10 mg/kg

13 - 15	5 mg/kg	5 mg/kg	15 mg/kg
16 - 18	7.5 mg/kg	7.5 mg/kg	15 mg/kg
19 - 21	7.5 mg/kg	7.5 mg/kg	20 mg/kg
22 - 28	10 mg/kg	10 mg/kg	20 mg/kg
29	7.5 mg/kg	7.5 mg/kg	20 mg/kg
30	7.5 mg/kg	7.5 mg/kg	15 mg/kg
31	5 mg/kg	5 mg/kg	15 mg/kg
32	5 mg/kg	5 mg/kg	10 mg/kg
33	2.5 mg/kg	2.5 mg/kg	10 ing/kg
34			5 ing/kg

35 - 37 off for 3 days then crossover

Weight			
Day	Morning	Afternoon	Evening
1 - 3			5 mg/kg
4 - 6	2.5 mg/kg	2.5 mg/kg	5 ing/kg
7 - 9	2.5 mg/kg	2.5 mg/kg	10
10 - 12	5 mg/kg	5 mg/kg	10 mg/kg
13 - 15	5 mg/kg	5 mg/kg	15 ing/kg
16 - 18	7.5 mg/kg	7.5 mg/kg	15 mg/kg
19 - 21	7.5 mg/kg	7.5 mg/kg	20 mg/kg
22 - 28	10 mg/kg	10 mg/kg	20 mg/kg
29	7.5 mg/kg	7.5 mg/kg	20 mg/lcg
30	7.5 mg/kg	7.5 mg/kg	15 mg/kg
31	5 mg/kg	5 mg/kg	15 mg/kg
32	5 mg/kg	5 mg/kg	10 mg/kg

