8.2 Recording of Adverse Events

At each contact with the subject, the investigator must seek information on adverse events by specific questioning and, as appropriate, by examination. Information on all adverse events should be recorded immediately in the source document, and also in the appropriate adverse event module of the case report form (CRF). All clearly related signs, symptoms, and abnormal diagnostic procedures results should be recorded in the source document, though should be grouped under one diagnosis.

All adverse events occurring during the study period must be recorded. The clinical course of each event should be followed until resolution, stabilization, or until it has been determined that the study treatment or participation is not the cause. Serious adverse events that are still ongoing at the end of the study period must be followed up to determine the final outcome. Any serious adverse event that occurs after the study period and is considered to be possibly related to the study treatment or study participation should be recorded and reported immediately.

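### Adverse events are to be recorded for 30 days after the last dose, but the last scheduled contact comes 4 to 5 days after it, leaving about 25 days with none

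*SAP*

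**What the plan says.** Section 8.1 of the SAP defines the adverse event reporting period as "the period from the initiation of any study procedures to the end of the study treatment follow-up" and adds that "the study treatment follow-up is defined as 30 days following the last administration of study treatment". Section 8.2 requires all events in the study period to be recorded, whether or not they are thought related, and sets the method of collection: "At each contact with the subject, the investigator must seek information on adverse events by specific questioning".

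The calendar is fixed in three places. The Study Summary states: "Subjects will receive drug for 34 days, and placebo for 34 days, with a 3 day washout period in between". The dosing table in Section 5.2 ends period 1 with "35 - 37 off for 3 days then crossover". The procedure outline in Section 6.0 has "Day 38 — Crossover".

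The last row of the Schedule of Events is a phone check on Day 76. Other contacts are mentioned without dates:

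- Step 15 of the outline has one call at completion about benefits and side effects of the second-round drug.
- Section 5.5, on compliance monitoring, has two-weekly calls that ask about adverse events. It does not say when they stop.
- The second bottle comes back at a routine appointment: "Once drug has been tapered the second time, patients will be instructed to return the bottle" at the next standard-of-care visit.

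Under its post-study heading, Section 8.1 has families told, at the last scheduled visit, to report later events that they or their physician believe may be related.

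**The concern.** The reporting period says which events count, and the contact schedule says when anyone asks about them. Here the second stops well before the first. For most of the 30 days after the period 2 drug, the plan schedules no contact at which the questioning required by Section 8.2 could take place. Capture then depends on families volunteering events.

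Safety is part of the primary hypothesis in Section 2.0, Section 1.5 names withdrawal symptoms as a reason for slow titration, and a stopping rule in Section 8.5 depends on identifying serious events attributable to gabapentin. If the report states that adverse events were collected to 30 days after the last dose, the schedule does not support that statement for period 2. A low count late in that window could mean few events or few questions.

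**Working it through.** **Inputs.** 34 dosing days per period and 3 days off (Study Summary, Section 5.2); crossover on Day 38 (Section 6.0); follow-up of 30 days after the last dose (Section 8.1); contacts on Days 0, 6, 13, 24, 28, 34-37, 38, 44, 51, 62 and 76 (Schedule of Events).

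**The plan's own figure.** Crossover day = 34 + 3 + 1 = Day 38, as stated.

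**Last dose in period 2.**
- If Day 38 is the first dosing day: 38 + 33 = Day 71.
- If Day 38 is day 0 of the period, as the call days suggest (44, 51 and 62 are 38 + 6, 38 + 13 and 38 + 24): 38 + 34 = Day 72.

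**Gap for a full second period.**

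| Quantity | Last dose Day 71 | Last dose Day 72 |
|---|---|---|
| Last dose to the Day 76 call | 76 - 71 = 5 days | 76 - 72 = 4 days |
| End of the 30-day window | 71 + 30 = Day 101 | 72 + 30 = Day 102 |
| Days after the last scheduled contact | 101 - 76 = 25 | 102 - 76 = 26 |
| Share of the window | 25/30 = 83% | 26/30 = 87% |

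**Early taper in period 2.** Step 10 allows an early taper after the Day 24 call, which is Day 62 in period 2. Assume it starts on Day 62 or 63 and takes 6 days, the length of the Day 29-34 taper in Section 5.2. The last dose is then Day 67 or 68, Day 76 is 9 or 8 days later, and 30 - 9 = 21 or 30 - 8 = 22 days remain. The gap shrinks but does not close.

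**By sequence.**
- Gabapentin first: the last gabapentin dose is Day 34, so its 30 days are Days 35-64. They hold the calls on Days 38, 44, 51 and 62, and the Day 34-37 visit unless it falls on Day 34 itself. From Day 38 the child is in the placebo period.
- Gabapentin second: only the Day 76 call falls in the 30 days.

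**The case against.** The strongest reply is that a reporting period defines what must be recorded, not when someone must telephone. A call can ask back over time, and the duty in Section 8.2 to record all events stands throughout. The two-weekly calls in Section 5.5 might continue past Day 76, the completion call might be placed later, and the routine appointment at which the bottle is returned might count as a contact. The related-events-only instruction sits under a post-study heading and does not replace that duty.

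Much of this stands. The figure of 25 days means no contact listed in the Schedule of Events; it does not mean that no contact could occur. But asking back needs a contact at or after the end of the window, and none is scheduled. The Section 5.5 calls sit under compliance monitoring and ask how the drug plan is working, so they may well end with dosing. The completion call and the appointment have no date. These texts leave the point unsettled.

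A reader might infer two stronger things that the document does not support.

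- *Post-gabapentin events are asked about in only one sequence.* The Day 76 call falls 4 to 5 days after the last dose and is a contact under Section 8.2, so both sequences are asked. The difference is how long the asking lasts.
- *The gabapentin-placebo comparison of adverse events is biased.* Section 7.2 plans no such comparison. The imbalance is between periods: placebo given second has the same single later contact as gabapentin given second. The contacts on Days 44, 51 and 62 after period 1 gabapentin fall in the placebo period, so events found then are not cleanly post-gabapentin. If the 3 days off are also counted after period 2 (Days 72-74 or 73-75), the Day 76 call comes after them, so the off-drug days the plan itself uses between periods are asked about in both.

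**Conclusion.** The conflict between Section 8.1 and the Schedule of Events is real. For a full second period, 25 or 26 of the 30 follow-up days come after the last scheduled contact; with an early taper it is 21 or 22, assuming a 6-day taper. As scheduled, contacts span the full 30 days after gabapentin only when gabapentin is given first. When it is given second, scheduled questioning ends 4 to 5 days after the last dose of a full period, and later events depend on spontaneous reports unless the undated contacts happen to fall late enough.

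This is incomplete safety capture after period 2. It does not show that gabapentin and placebo are treated differently within a period, or that events in the first days off drug are missed. The conclusion rests on reading the Schedule of Events as the full list of dated contacts.

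**What to change.** Choose one and make the sections agree:

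1. Add one adverse event phone check at the end of the 30-day window, about Day 101, to the Schedule of Events. Date it from the actual last dose so that an early taper is covered. State in Section 5.5 when the two-weekly calls stop, and in step 15 of Section 6.0 whether the completion call is the Day 76 call or the new one.
2. Or restate the reporting period in Section 8.1 to end at the last scheduled contact, and say that later events are collected only if reported spontaneously.

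Under either option, if adverse events are tabulated by treatment, count those starting from the first dose to the end of washout in each period. That is 34 + 3 = 37 days in both, if the 3 days off are also applied after period 2.

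Option 1 costs one call per family and about 25 more days of follow-up. Option 2 is a short text change, but it gives up the claim to 30 days of complete capture.
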